6.0 Randomization of Patients

6.1 Patients will be randomized at the time of registration/enrollment on this clinical trial via contact with the study nurse/coordinator at the time of the initial registration of the subject. The study statistician ([name]) will conduct the randomization and relay this information to the study nurse who will be in contact with the treating/enrolling physician so that the appropriate medication (prednisone or cyclosporine) may be immediately started with PE.

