14.0 Statistical Analysis

14.1 Statistical Considerations-Sample Size Determination

For the study of the primary endpoint (treatment success rate), the sample size required is calculated based on the data from our previous publications. In these previous studies that looked separately at CSA/PE in 10 patients and at corticosteroids/PE in another 10 patients, we saw promising results that led to our hypothesis that CSA/PE treatment for TTP patients results in greater treatment response. In those studies, the primary endpoint was the proportion of patients who had TTP exacerbation, which is a more stringent endpoint that does not include other types of treatment failures such as refractory patients and/or death within 30 days post-PE. In the previous published pilot studies, we showed that 6/10 corticosteroid-treated patients exacerbated versus 0/10 CSA-treated patients. Combined with experience with subsequently treated patients, we observed an overall treatment success rate of 80% and 83% in refractory vs. de novo TTP patients, respectively, treated with CSA+PE versus 33% in those treated with corticosteroids+PE.

In terms of our primary endpoint of treatment success rate, we have designed a phase III trial that compares the proportion of treatment successes in each arm. Specifically, this study design will have at least 80% power to determine a significant difference in the treatment success rates between the arms if the true rates are 50% vs. 80%, assuming a significance level of 0.05 and a two-sided test. This reflects a clinically meaningful difference, and the data from our previous studies and experience support it as a feasible difference to detect. We plan to enroll a total of 72 patients to this trial (36 to each arm) to test the null hypothesis that there is no difference in treatment success rate between these treatments.

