14.2 Analysis Plan

Patients will be followed for 30 days after their last PE procedure unless a treatment failure has been documented prior to that timepoint. The treatment success rates will be calculated for each of the treatment arms along with their 95% confidence intervals. These proportions will be compared between treatment arms using Mantel-Haenszel chi-square test to accommodate the

stratification factor (recurrent vs. de novo TTP event). Statistical significance will be concluded based on a significance level of 0.05.

This study includes an interim analysis and formal “look” at the data after 24 patients have been accrued (12 to each arm), where the null hypothesis will be rejected if the calculated p-value comparing the two observed success rates for the treatment arms is <0.0002 (based on the Lan-DeMets alpha spending function and O’Brien-Fleming boundary calculation). We will also evaluate safety and tolerability data for each of the arms at the interim analysis, and these data will be reviewed not only by the study team but by the DSMB.

Through this study we also planned an internal pilot study to be completed after 12 patients have been accrued (6 to each arm) in an effort to obtain information on the feasibility of accrual and treatment follow-up for the endpoints; as an internal pilot study, all patients will be included in the overall trial and thus included in the interim and final analyses unless serious logistical issues were identified that would introduce bias by their inclusion. We reached the accrual point for this internal pilot study and no such logistical issues were identified; therefore, all patients will be included in the overall study. With so few patients, this internal pilot was used for assessment of feasibility; the early data were not formally evaluated and did not require a re-evaluation of our assumptions for the study design described above.

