Additionally, we will evaluate several secondary clinical endpoints through this trial, including: 1) exacerbation rate within 30 days post-PE; 2) clinical response rate; 3) the number of PE procedures required to achieve a clinical response; 4) relapse rate; and 5) safety and tolerability of each of the adjuvant treatments to PE. Each of the rates will be calculated assuming that these endpoints are binomially distributed, and 95% confidence intervals generated. For the exacerbation rate endpoint, we will only include those patients who have achieved clinical response (i.e. excluding refractory patients) and compare these rates between the two arms. We will have at least 80% power to detect a difference if the true exacerbation rates are 55% vs. 90% for this subset analysis (not adjusting for multiple comparisons); however, this comparison is distinctly ancillary to our primary clinical interest of achieving treatment success in all patients treated versus only keeping responding patients from experiencing TTP exacerbation. We will also evaluate relapse as a time-to-event variable, where Kaplan-Meier methods will be used to assess time to relapse from last plasma exchange in responding patients. The number of exchange procedures required to achieve clinical response will be assessed between arms using Poisson regression. Safety and tolerability data will be summarized by type of adverse event with frequencies calculated and compared between arms. In addition to these planned quantitative analyses, we will also use graphical

analyses to assess patterns and differences in these factors between the treatment arms.

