14.3 Statistical Considerations-Correlative Laboratory Studies

The correlative biomarker outcomes described above will be descriptively summarized across and within treatment arms, and patterns in these changes in biomarkers and how they relate to treatment success, relapse, and TTP exacerbation will be explored graphically. For the study to determine the effects of corticosteroids and cyclosporine given individually on serial measurements of ADAMTS13 biomarker profiles and VWF multimeric patterns after their initial therapy and throughout longitudinal follow-up, we will evaluate these biomarkers in relation to the clinical outcomes of interest. For treatment success rates, we will evaluate baseline levels of these biomarkers to identify if there are any associations between these biomarkers and how these patients respond to treatment. These will first be explored graphically, also denoting those patients in the two different treatment arms. Logistic regression for whether or not the patient had a treatment success will be modeled with these baseline biomarkers as well as treatment arm.

In addition, we will compare the changes for each biomarker between the two groups. TTP exacerbations and relapses will be modeled separately. Both of these events are preceded by a period of clinical response where patients exhibit resolution of clinical signs and normal laboratory values. However, as stated above, there are important differences that warrant modeling TTP exacerbation and TTP relapses independently. First, the frequencies of specimen collection are different between the observation periods that lead to the exacerbation and relapses. The patients in the period of initial clinical response are monitored weekly, while the patients in the sustained clinical remission are followed quarterly. Secondly, the underlying pathophysiology for exacerbation and relapse are likely to be different. The disease exacerbation probably represents a continuation of an incompletely resolved disease while relapses of TTP most likely represent a de novo episode of TTP. As a result, the biomarkers that predict TTP exacerbation and relapse are likely to be different.

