Since each individual has several observations, possibly with and without relapse or exacerbation, this would induce a special correlation structure. For this reason, we will introduce random effects into the model (53-55). The covariates corresponding to gender, age, race, and treatment modalities (e.g. CSA vs. corticosteroids) will also be evaluated in the model. Additionally, various variance-covariance structures will be investigated. The Generalized Estimation Equation will also be used if necessary if our specific covariance structures lead to un-interpretable results. Since the number of predictor variables is relatively small, a standard traditional model selection procedure will likely be feasible to study the reach of the predictors as well as their interacting effects. Various model selection criteria such as Ra2, Mallows Cp, AIC, and BIC will be used to evaluate the putative models. In the case where samples are not available on all subjects at consistent timepoints, we will utilize the more flexible growth curve modeling approach to identify changes over time in the biomarker on the incidence and time to relapse as well as TTP exacerbation.

VWF multimer patterns form a relatively complex dataset. We will dissect VWF patterns into several parameters that will all give rise to a continuous measurement. This will be the density of VWF multimers in bands 1 through 15 and the area above band 15. All data will be normalized by the reference plasma included in each gel. For investigating the relationship between ULVWF (area above band 15) and relapse in the quarter immediately following, a logistic regression analysis as described will be performed. Specifically, the response variable will be 1 or 0, depending on whether relapse has occurred or not. The explanatory variable will be the ULVWF value at the beginning of the quarter-interval, with a random effect also included to account for correlations among the different response variable observations over time in a given patient. The effects of other covariates will be included in the model and adjusted for as necessary.

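### Recurrent versus de novo TTP stratifies the primary test but is named in no secondary arm comparison or marker model, so a marker that only tracks disease history could look prognostic

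*Combined protocol and SAP*

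**What the plan says.** Section 14.2 compares treatment success between arms with a Mantel-Haenszel test that takes account of the "stratification factor (recurrent vs. de novo TTP event"). This is the factor's only mention in the document.

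- **Secondary arm comparisons (14.2).** For exacerbation, "we will only include those patients who have achieved clinical response (i.e. excluding refractory patients) and compare these rates"; no test or stratum is named. Response and relapse rates get binomial intervals. The exchange count is compared between arms by Poisson regression. Time to relapse is described by Kaplan-Meier methods, with no test named.
- **Baseline marker model (14.3).** "Logistic regression for whether or not the patient had a treatment success will be modeled with these baseline biomarkers as well as treatment arm". No other term is listed.
- **Longitudinal exacerbation and relapse models (14.3).** "The covariates corresponding to gender, age, race, and treatment modalities (e.g. CSA vs. corticosteroids) will also be evaluated in the model". Random effects are added, and models are chosen by criteria such as AIC and BIC.
- **ULVWF model (14.3).** Other covariates are to be adjusted for where needed; none is named.
- **Randomisation (6.0).** "Patients will be randomized at the time of registration/enrollment on this clinical trial via contact with the study nurse/coordinator". No strata or blocks are described.

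Section 5.2.5 admits patients with a previous TTP diagnosis. Their expected share is not given.

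**The concern.** The plan treats recurrent versus de novo as important enough to stratify the main test, then does not mention it where disease history is most likely to matter. Section 2.3 links persistent or recurrent inhibitors to recurrence and a chronic relapsing course, and reports that lower ADAMTS13 activity goes with more exacerbations and relapses. So previous TTP may plausibly relate both to the markers and to the outcomes. Section 2.3 does not quantify that link.

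Section 1.2 lists finding markers prognostic for exacerbation and relapse as an objective. A marker that merely separates patients with earlier episodes from first-episode patients tells the clinician nothing that the history does not. The listed covariates (gender, age, race, arm) cannot reveal this. For the arm comparisons, the stake is a possible small loss of power and an analysis that does not match the primary one.

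**Working it through.** **1. The plan's own figure.** Section 14.1 sets the power target at 80% or more, with these inputs: "if the true rates are 50% vs. 80%, assuming a significance level of 0.05 and a two-sided test". On enrolment it says: "We plan to enroll a total of 72 patients to this trial (36 to each arm"). The unpooled two-proportion formula gives n = (1.960 + 0.842)² × (0.25 + 0.16) / 0.30² = 35.8, so 36 per arm with 80.3% power. The figure reproduces. The pooled formula would need 39 per arm and gives 77.2% at 36, which is why the simulated powers below start near 77%.

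**2. Inputs for the marker models.**
- From 14.3: more than 400 quarterly observations and about 16 relapses; about 200 weekly observations and about 16 exacerbations.
- Layout used: 50 patients × 8 quarters at a 4% event rate (400 × 0.04 = 16 events), and 54 patients × 4 weeks at 7.5% (216 × 0.075 = 16.2 events).
- Assumed, because the documents do not give them: 40% recurrent; stratum odds ratio (OR) for the event; marker shift in recurrent patients in SD units; within-patient marker correlation 0.6; patient intercept SD 0.5.
- The marker has no effect of its own. Each model holds arm and marker, without or with the factor. Nominal level is 5%.

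**3. False-positive rate for the null marker, factor left out / factor included (%).**

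| Stratum OR | Marker shift | Relapse, no random effect | Relapse, random intercept | Exacerbation, random intercept |
|---|---|---|---|---|
| 4 | 1 SD | 20.8 / 4.5 | 16.5 / 4.7 | 18.5 / 5.8 |
| 4 | 0.5 SD | 10.5 / 4.7 | 8.8 / 4.8 | 10.0 / 6.0 |
| 2 | 1 SD | 9.2 / 5.0 | 8.0 / 4.8 | 9.3 / 6.0 |
| 1.23 | 1 SD | 3.5 / 3.9 | 5.8 / 5.8 | 5.2 / 4.7 |
| 4 | none | 5.4 / 4.6 | 5.8 / 5.0 | 6.2 / 5.0 |
| 1 | 1 SD | 5.3 / 5.3 | 5.8 / 5.2 | 5.8 / 5.8 |

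The random-intercept columns rest on 600 runs each, so the standard error is √(0.05 × 0.95 / 600) = 0.9 points near 5% and √(0.165 × 0.835 / 600) = 1.5 points at 16.5%. The other column has about 1,500 runs. A random intercept does not cure the problem, because it is assumed independent of the marker and the omitted factor breaks that assumption. The last two rows show no inflation when either association is missing.

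**4. Power of the arm comparison, Mantel-Haenszel test without / with strata (%).** 40% recurrent, balanced by arm, 40,000 runs per setting. The exacerbation case reads the 55% versus 90% of section 14.2 as exacerbation-free rates, hence 45% versus 10% exacerbating, and assumes 30 responders per arm.

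| Stratum OR | 50% vs 80%, 36 per arm | 45% vs 10%, 30 per arm |
|---|---|---|
| 1.23 | 77.2 / 77.6 | 89.4 / 89.5 |
| 2 | 77.7 / 78.8 | 89.4 / 89.9 |
| 4 | 77.9 / 81.1 | 90.0 / 91.4 |
| 8 | 79.4 / 84.2 | 91.0 / 93.8 |

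The gain is 0.1 to 1.1 points at OR up to 2, 1.4 to 3.2 at OR 4, and 2.8 to 4.8 at OR 8.

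**5. Size of the unstratified test.** With 64 responders, 40% recurrent and event risks of 65% versus 15%, the unstratified test has size 2.1% if the strata are balanced by arm and 5.3% under simple randomisation. It is conservative only in the first case.

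**6. Model size.** Four markers plus gender, age, race and arm make at least 8 terms, or 16 / 8 = 2 events per term before interactions. One more gives 16 / 9 = 1.8.

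**The case against.** *Silence is not omission.* This is right in part. The ULVWF model allows further covariates, and section 14.2 names no test for exacerbation or response, so a reader might infer that every marker model leaves the factor out and every secondary test is unstratified, but the text does not say so. It supports only that none of them names the factor. The baseline model and the main longitudinal models do list their terms, and the factor is not among them.

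*The power loss needs a very strong factor.* This stands. A reader might infer a material loss of power. Risks of 75% versus 40% in recurrent and 25% versus 8% in de novo patients do give 55% power unstratified and 64% stratified, but they imply stratum odds ratios of (0.75/0.25)/(0.25/0.75) = 9 and (0.40/0.60)/(0.08/0.92) = 7.7. No passage supports such values. The nearest figure, 80% versus 83% success on CSA in section 14.1, gives (0.83/0.17)/(0.80/0.20), about 1.2. It contrasts refractory with de novo patients, so it shows neither that the factor is weak nor that it is strong.

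*A conservative unstratified test cannot be assumed.* This also stands: it requires randomisation balanced on the factor, and section 6.0 does not describe that.

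*The aim is prediction.* A marker correlated with relapsing history does predict relapse, and calling that a false positive presumes that added value is the question. If history acts only through the inhibitor, leaving it out causes no bias: a check with a true marker effect of -0.80 gave -0.796 without the factor and -0.794 with it. Both points limit the interpretation. Neither argues against adjusting, since the adjusted estimate was equally good there and the documents do not say which mechanism holds.

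*These analyses are ancillary.* True, and the primary conclusion is untouched. Prognostic markers are nonetheless a listed objective.

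**Conclusion.** The point holds in conditional form. The factor that stratifies the primary test is named in no secondary arm comparison and no marker model, and the baseline and main longitudinal models list other terms without it.

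The marker models are the part that matters. If previous TTP relates to both marker and outcome, the chance that an uninformative marker is declared prognostic rises from about 5% to 8-11% under moderate assumptions and to 17-21% under strong ones. It does not rise if either association is absent. The direction follows from ordinary confounding; the size rests on an assumed 40% recurrent share and assumed associations, so confidence in the magnitude is low.

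For the arm comparisons the benefit of stratifying is consistency with the primary test and a small gain in power, not the repair of an invalid test.

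**What to change.** - In section 14.3, make recurrent versus de novo a pre-specified covariate, exempt from model selection, in the treatment-success, exacerbation, relapse and ULVWF models. Listing it as one more candidate is not enough, because selection could drop it.
- In section 14.2, apply the primary test's Mantel-Haenszel stratification to the exacerbation and response rates. Add the factor to the exchange-count regression, and to any arm comparison of time to relapse (stratified log-rank test or Cox model).
- In section 6.0, state whether randomisation is stratified on this factor.
- Where a marker's unadjusted prediction is also of interest, report it beside the adjusted estimate and label it as such.

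The primary test already requires the variable, so no new data are needed. The cost is SAP wording and one degree of freedom per model. With about 16 events that is not negligible, so this term should come before data-driven selection among the other covariates and interactions.

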1.0 OBJECTIVES

This will be a multi-center, open-label, randomized study that directly compares the use of cyclosporine and plasma exchange to corticosteroids and plasma exchange as the initial treatment of patients with thrombotic thrombocytopenic purpura. This study has the following objectives:

Primary Objective

1.1 To determine if cyclosporine given individually as an adjunct to plasma exchange decreases the rate of exacerbation in patients with TTP compared to corticosteroids given as an adjunct to plasma exchange.

Secondary Objectives

1.2 To compare the CSA and PE treatment arm to the corticosteroid and PE treatment arm with respect to:

- exacerbation rate within 30 days post-PE
- clinical response rate
- number of exchange procedures to achieve clinical response
- relapse rate (recurrent disease >30 days after last PE)
- safety data for CSA as an adjunct to PE.
- the effects of corticosteroids vs. cyclosporine on ADAMTS13 antigen, activity, and ADAMTS13 antibody concentration and inhibitor titers using serial measurements both during and after discontinuation of study drug
- the VWF multimeric patterns after initial therapy and throughout longitudinal follow-up between the two treatment arms
- the laboratory biomarker(s) that are prognostic for TTP exacerbation and the risk of relapse

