To examine the potential of the 4 indices (ADAMTS13 activities, ADAMTS13 antigen levels, ADAMTS13 (IgG) autoantibody levels, and antibody inhibitor titers) to predict the recurrences of TTP, we will use the longitudinal data in two ways by separating indices obtained during the sustained clinical remission when they are measured every three months (quarterly) from those indices measured during the initial clinical response when patients are monitored weekly. The data for the relapse analysis will come from all quarterly samples collected from qualified study subjects during sustained remission. The outcome of interest will be whether or not the

individual experiences a relapse of TTP during the three months following the date the measurements are taken. We anticipate obtaining a total of >400 observations that will correspond to approximately >16 events of relapse and other quarterly measurements ($n \sim 400$) without relapses. For analysis of exacerbation in initial clinical remission, the outcome of interest will be whether or not the individual experiences an event of exacerbation in the week following the measurement. The weekly samples in initial clinical remission from the same group of study subjects will be analyzed. We anticipate a total of about 200 weekly data points, corresponding to about >16 measurements with events of exacerbation and 200 measurements without events in the week following measurement. We will use the logistic regression model to analyze all 4 indices independently as well as to evaluate their interacting effects.

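### The prognostic biomarker models in section 14.3 have about 14 candidate terms for about 16 events, and two of the four listed selection criteria do not fit the model; noise markers are likely to be selected unless BIC or a prespecified model governs

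*Combined protocol and SAP*

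**What the plan says.** Section 1.2 lists among the secondary objectives a comparison covering "the laboratory biomarker(s) that are prognostic for TTP exacerbation and the risk of relapse". Section 14.3 gives the analysis, with separate models for relapse (quarterly samples) and exacerbation (weekly samples).

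- **Events.** For relapse, more than 400 quarterly observations with roughly 16 or more events. For exacerbation, about 200 weekly data points, "corresponding to about >16 measurements with events of exacerbation and 200 measurements without events in the week following measurement".
- **Predictors.** Four ADAMTS13 indices (activity, antigen, IgG autoantibody, inhibitor titer): "We will use the logistic regression model to analyze all 4 indices independently as well as to evaluate their interacting effects". Then: "The covariates corresponding to gender, age, race, and treatment modalities (e.g. CSA vs. corticosteroids) will also be evaluated in the model".
- **Model.** Because patients contribute repeated observations: "For this reason, we will introduce random effects into the model". GEE is the fallback if the covariance structures give results that cannot be interpreted.
- **Selection.** "Since the number of predictor variables is relatively small, a standard traditional model selection procedure will likely be feasible". And: "Various model selection criteria such as Ra2, Mallows Cp, AIC, and BIC will be used to evaluate the putative models".

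Section 14.3 names no lead criterion and no order of interaction. It sets no limit on model size and provides no shrinkage, internal validation or multiplicity rule for these models.

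**The concern.** There are three linked difficulties.

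1. The case for model selection rests on the predictor count being small. What matters for a logistic model is the count relative to events, and events are few.
2. Adjusted R2 and Mallows Cp are built from residual sums of squares in linear regression. They have no standard meaning for a binary random-effects model. AIC and BIC need a likelihood, so they do not carry over to GEE. Under the fallback, none of the four listed criteria fits.
3. The four criteria differ greatly in how readily they keep a useless term. With no lead criterion, the choice can be made after the data are seen.

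At stake is the reliability of the answer to a listed secondary objective: a marker could be put forward as prognostic because of the selection procedure alone, with an apparent discrimination that would not hold up in new patients.

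**Working it through.** **Plausibility of the plan's event count.** Section 14.3 gives no derivation. Section 14.2 quotes 55% vs. 90% for the exacerbation comparison; I read these as exacerbation-free rates (an assumption), so exacerbation rates of 45% and 10%. With 72 patients and response of 10/12 to 11/12 (the pilot cohorts in sections 2.6 and 3.2), there are 60 to 66 responders:

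- 30 × 0.45 + 30 × 0.10 = 16.5
- 33 × 0.45 + 33 × 0.10 = 18.2

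So just over 16 exacerbations is consistent with the plan. The relapse count cannot be checked, because no relapse rate is given.

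**Terms and events per term.** Four indices + C(4,2) = 6 pairwise interactions + 4 covariates (race as one term) = 14. Pairwise order and single-term race are assumptions that keep the count low.

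- 16 events: 16/14 = 1.14 per term
- 20 events: 20/14 = 1.43
- 32 events: 32/14 = 2.29

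**Chance of keeping a noise marker.** A one-degree-of-freedom noise term is kept approximately when its chi-square statistic exceeds the criterion's penalty: 1 for adjusted R2, 2 for AIC or Cp, ln(n) for BIC. For k independent noise terms, P(at least one kept) = 1 − (1 − p)^k.

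| Criterion | p per term | 10 marker terms | 4 main effects only |
|---|---|---|---|
| Adjusted R2 | 0.317 | 97.8% | 78.3% |
| AIC or Cp | 0.157 | 81.9% | 49.6% |
| BIC, n = 216 observations | 0.020 | 18.6% | 7.9% |
| BIC, n = 416 observations | 0.014 | 13.2% | 5.5% |
| BIC, n = 72 patients | 0.039 | 32.6% | 14.6% |

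For example, under AIC: 1 − 0.843^10 = 82% and 1 − 0.843^4 = 50%. The observation counts are 200 + 16 and 400 + 16.

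**Simulation check.** Null data with 16 events in 216 or 416 records, marker correlation 0 or 0.5, backward elimination from all 14 terms, 250 replicates per setting. The share keeping at least one of the ten marker terms was 97-98% (adjusted R2), 78-82% (AIC), 76-82% (Cp) and 11-18% (BIC). With 32 events in 416 records (200 replicates), AIC still gave 79-81%. The full 14-term noise model had an apparent AUC of about 0.75 at 16 events. AIC and BIC were applied to ordinary logistic fits, adjusted R2 and Cp to least-squares fits of the binary outcome; no random intercept was fitted.

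**Structure of the exacerbation records.** Section 8.4.1 defines exacerbation by restart of plasma-based therapy within 30 days of stopping PE. About 216 weekly records over at most 72 patients is about 3 each, a short run of zeros ending in at most one event. That is a discrete-time hazard, so time since last PE belongs in the model; section 14.3 does not list it. Relapse differs: section 8.5.2 keeps relapsed patients in follow-up, so repeat events are possible.

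**Single-index alternative.** One index per model gives 16/1 = 16 events per marker term; with arm added, 16/2 = 8; with week as one linear term, 16/3 = 5.3. Four tests at 0.05: 1 − 0.95^4 = 18.5% chance of at least one false marker if independent. At 0.0125 each: 1 − 0.9875^4 = 4.9%.

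**The case against.** The strongest reply is that section 14.3 is correlative work. It speaks of descriptive summaries, graphical exploration and putative models, and sets no alpha or decision rule for them. It also analyses the indices one at a time, where events per term are adequate, and its GEE fallback would normally bring patient-cluster robust standard errors. The 14-term model is a count of what the text allows: the plan specifies neither a single full model nor backward elimination. Most of this stands and limits the point. It does not answer the absence of a lead criterion, or the listing of two criteria that do not fit the model.

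Three stronger readings are tempting and are not supported.

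- *The linear-model criteria are what produce false markers.* AIC, which is valid for a likelihood-fitted logistic mixed model, gives the same 82% as Cp. The risk comes mainly from many terms, few events and free choice of criterion; deleting the two criteria alone would not remove it.
- *Noise markers will be reported as prognostic.* BIC is on the same list and gives 13-19% with n as observations. Being kept by a criterion is also not the same as being reported as prognostic.
- *The patient random effect is unworkable.* No fit or simulation was run to show this. A discrete-time hazard can include a frailty term, and for relapse a random effect is reasonable.

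**Conclusion.** The point holds in a limited form. Calling the predictor set small is not supported by the plan's own event counts: about 14 terms against about 16 events, or 1.1 per term. Two of the four criteria do not apply to the planned model, and none of the four applies to the fallback. If all markers are noise, the chance of keeping at least one runs from 13% to 98% depending on which criterion is used, so noise selection is likely unless BIC or a prespecified model governs.

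The figures assume pairwise interactions, race as one term, independent terms in the formula, and no random intercept in the simulation. With main effects only, AIC falls to about 50%. The plan gives 16 as a lower bound, but doubling the events hardly changes the AIC result. This should be corrected because it bears on a listed secondary objective. It does not touch the primary endpoint.

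**What to change.** Amend section 14.3 as follows.

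1. Delete adjusted R2 and Mallows Cp.
2. Make the single-index models, already foreseen, the prespecified analysis: one model per index, adjusted for treatment arm, using penalised (e.g. Firth) logistic likelihood or GEE with patient-cluster robust standard errors.
3. Add week since last PE to the exacerbation model. The random effect may stay for relapse.
4. Apply a multiplicity adjustment across the four indices (e.g. 0.0125 each), or label the results exploratory. Without one of these, single-index testing at 0.05 carries about the same false-marker risk as BIC selection with n = 216.
5. Report interactions and any multi-marker model as exploratory, with discrimination corrected for optimism by a bootstrap that resamples patients.

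Cost: SAP wording and modest extra analysis work, with no change to data collection. The downside is that fewer markers and interactions can be claimed.
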